2.2. Secondary Objectives

The secondary objectives of the study are as follows:

- To assess emergence of antibodies against the drug product as well as OX40 ligand (OX40L), the protein translated by the drug product
- To assess mRNA PK alone and in combination with durvalumab
- To assess anti-tumor effects of mRNA-2416 alone and in combination with durvalumab
- Phase I only: To assess objective response rate and duration of response (DOR) of mRNA-2416 alone and in combination with durvalumab based on RECIST v1.1 or Cheson 2014 criteria (lymphomas)
- Phase II only: To assess disease control rate (DCR) and DOR of mRNA-2416 alone and in combination with durvalumab based on RECIST v1.1

2.3. Exploratory Objectives

The exploratory objectives of the study are as follows:

- To assess objective response rate of mRNA-2416 alone and in combination with durvalumab based on Immune-related Response Criteria (irRC) or lymphoma response to immunomodulatory therapy criteria (LYRIC)
- To assess the correlation of other investigational serum-based proteins (eg, anti-drug antibodies) with PK, efficacy, and safety endpoints
- To assess biomarkers of immunological response in tumor and blood of mRNA-2416 alone and in combination with durvalumab
- To assess PK of durvalumab in combination with mRNA-2416

3. Investigational Plan

3.1. Overall Study Design and Plan

This is an open-label, multicenter, Phase I/II Dose Escalation study of repeated intratumoral injections of mRNA-2416 alone (Arm A) and in combination with intravenously administered durvalumab (Arm B) in patients with advanced relapsed/refractory solid tumor malignancies or lymphoma, followed by Expansion period in patients with ovarian cancer in each treatment arm. Each arm of the study consists of a Dose Escalation Period in non-visceral lesions and a Dose Confirmation period in visceral lesions followed by a Dose Expansion Period in ovarian cancer.

Each dose level in the Dose Escalation Period will be conducted using a standard 3+3 study design in order to determine the safety and tolerability of each dose. For Arm A Dose Escalation, once a dose level has been cleared for safety, that dose level is open to enrollment of up to 9 additional patients who are willing and eligible to undergo tumor biopsy.

Once the expected MTD/RDE has been cleared in Dose Escalation for Arm A, Dose Escalation in Arm B will begin with mRNA-2416 at 1 dose level lower than the Arm A MTD/RDE according to the protocol Table 1.

For both arms, once the expected MTD/RDE has been cleared in Dose Escalation, Dose Confirmation of the MTD/RDE will be conducted in at least 3 patients with ovarian cancer with visceral lesions injectable

with ultrasound or computer tomography (CT) guidance. Dose Confirmation will be conducted in the same fashion as Dose Escalation.

For both arms, once the MTD and/or RDE has been determined in Dose Escalation/Confirmation, patients will be enrolled in the Expansion cohort in order to assess the preliminary anti-tumor activity of mRNA-2416 in ovarian cancer of epithelial origin.

Prior to enrollment, all patients will undergo screening to determine study eligibility. Arm A patients will receive mRNA-2416 for 6 cycles with 28 days in each cycle. Arm B patients will receive mRNA-2416 in combination with durvalumab for 6 cycles with 28 days in each cycle. Following completion of 6 cycles of combination dosing, patients may continue with durvalumab as a single-agent until disease progression, unacceptable toxicity, or 24 months of treatment (total), whichever is sooner. Patients completing study therapy with an overall tumor assessment of stable disease (SD) or better will be followed for efficacy for 6 months or until disease progression, whichever occurs first. Schedule of events can be found in the protocol.

3.2. Study Endpoints

3.2.1. Primary Endpoints

The primary endpoints of the study are as follows:

Phase I

- Incidence and nature of dose-limiting toxicities (DLTs) with mRNA-2416 alone and in combination with durvalumab
- Incidence, nature, and severity of adverse events (AEs)/serious adverse events (SAEs), graded according to the National Cancer Institute (NCI) Common Terminology Criteria for Adverse Events (CTCAE) Version 4.03 for mRNA-2416 alone and in combination with durvalumab

Phase II

- Assessment of objective response rate mRNA-2416 alone and in combination with durvalumab in patients with ovarian cancer based on RECIST v1.1

3.2.2. Secondary Endpoints

The secondary endpoints of the study are as follows:

- Presence and/or concentration of antibodies against the drug product as well as OX40L, the protein translated by the drug product
- Phase I only: Assessment of objective response rate, DOR, and progression-free survival (PFS) of mRNA-2416 alone and in combination with durvalumab based on RECIST v1.1 or Cheson 2014 criteria (lymphomas)

- Phase II only: Assessment of DCR, DOR, and PFS of mRNA-2416 alone and in combination with durvalumab in patients with ovarian cancer based on RECIST v1.1
- PK parameters for mRNA-2416 alone and in combination with durvalumab: maximum observed concentration (C_{max}) and area under the concentration-time curve (AUC)

3.2.3. Exploratory Endpoints

The exploratory endpoints of the study are as follows:

- Assessment of objective response rate of mRNA-2416 alone and in combination with durvalumab based on irRC or LYRIC
- Assessment of the correlation of other investigational serum-based proteins (eg, anti-drug antibodies) with PK, efficacy, and safety
- Evaluation of plasma will include assessment of pro-inflammatory cytokines and interferons
- Evaluations of tumor tissue will include:
 - Expression of OX40 and OX40L and change in expression over the treatment period
 - Expression of other immune-related markers, including programmed death 1 (PD-1) and programmed death ligand 1 (PD-L1)
 - Infiltration of tumor with immune effector cells, including T cells
- PK parameters for durvalumab in combination with mRNA-2416: C_{max} and AUC

The on-treatment biopsy timing may be adjusted based on emerging data.

Where possible, outcome measures will be correlated with clinical characteristics such as tumor histotype, dose of mRNA administered, and clinical outcomes.

3.3. Treatment

Two investigational products, mRNA-2416 and durvalumab, are tested on patients with advanced relapsed/refractory solid tumor malignancies or lymphoma. mRNA-2416 is a novel mRNA encoding human OX40L encapsulated in a lipid nanoparticle, administered through repeated intratumoral injections on tumor lesions. Durvalumab in combination with mRNA-2416 in arm B is administered to study patients through intravenous infusion.

Arm A patients receiving treatment to superficial lesions will receive mRNA-2416 on Day 1 and Day 15 of a 28-day cycle for 6 cycles. Arm A patients receiving treatment to visceral lesions and all Arm B patients will receive mRNA-2416 on Day 1 and Day 15 for Cycle 1, and on Day 1 only for Cycles 2-6. All Arm B patients will receive durvalumab in combination with mRNA-2416 on Day 1 in each cycle. Dose levels of mRNA-2416 can be found in the protocol Table 1 and Table 2. In the event that ≥ 2 of the first 6 DLT-evaluable patients in the 8.0 mg cohort experience a DLT, an intermediate dose cohort may be opened at 6.0 mg mRNA-2416. Per protocol, the potential dose cohorts are 0.5 mg, 1.0 mg, 2.0 mg, 4.0

mg, 6.0 mg, and 8.0 mg of mRNA-2416 alone, and 2.0 mg, 4.0 mg, 6.0 mg, and 8.0 mg of mRNA-2416 in combination with durvalumab. Some cohorts may not have any patients enrolled during the course of the study. Only the dose cohorts that have patients enrolled will be analyzed. If the dose level of mRNA-2416 that a patient received at the first dose is different from the dose cohort that the patient was enrolled in, the patient may be analyzed in the dose level of mRNA-2416 that the patient received as specified in the analysis.

Following are the potential treatment arms and dose cohorts for Phase I and Phase II.

- Arm A
 - mRNA-2416 0.5 mg
 - mRNA-2416 1.0 mg
 - mRNA-2416 2.0 mg
 - mRNA-2416 4.0 mg
 - mRNA-2416 6.0 mg
 - mRNA-2416 8.0 mg
- Arm B
 - mRNA-2416 2.0 mg + Durvalumab
 - mRNA-2416 4.0 mg + Durvalumab
 - mRNA-2416 6.0 mg + Durvalumab
 - mRNA-2416 8.0 mg + Durvalumab

4. General Statistical Considerations

This document will provide details regarding the definition of analysis variables and analysis methodology to address all study objectives.

Unless otherwise specified, the first/last dose refers to the first/last dose of study drug (mRNA-2416 or durvalumab). Study day for events on or after the date of the first dose will be defined as the number of days from the date of the first dose, plus 1 day, so that the date of the first dose will be defined as Day 1. For events before the date of the first dose, study day will be calculated as the difference in days between the date of the first dose and the date of interest. Thus, the day before the date of the first dose will be defined as Day -1. This means there will be no study Day 0.

Baseline is defined as the last assessment prior to the first dose. All baseline measurements must have been collected prior to administration of the first dose. Measurements obtained after the first dose will be considered as post-baseline values. If the measurement of a variable is not made on a given patient prior to the first dose, that patient will be considered not to have a baseline value for that variable. Change from baseline is defined as post-baseline assessment minus baseline assessment.

Continuous data will be described using the following descriptive statistics: the number of patients (n), mean, standard deviation, median, minimum and maximum, where appropriate. Categorical data will be summarized using the frequency count (n) and percentage (%) of patients for each category, where appropriate. Percentages will be based on non-missing data unless specified otherwise.

Unless otherwise specified, all statistical tests will be 2-sided and conducted at the 0.05 significance level.

No imputation will be applied for missing data unless otherwise specified.

All collected data used for safety and efficacy evaluations will be presented in listings. Data will be displayed in all listings sorted by treatment arm, cohort (dose escalation/confirmation/expansion), dose cohort, and patient identifier unless otherwise specified.

The Medical Dictionary for Regulatory Activities (MedDRA) will be used for coding AEs and medical histories. Prior or concomitant medication data will be coded using the World Health Organization (WHO) Drug Dictionary.

4.1. Sample Size

No formal sample-size estimation will be performed. The choice of the number of patients will be based on a standard, Phase 1, 3+3 dose escalation design in which 3 to 6 patients are enrolled into each dose cohort.

For the Arm A dose expansion period, the sample size estimation is based on Simon's minimax two-stage design (Richard S, 1989). The null hypothesis that the true overall response rate (ORR) is 0.05 will be tested, and the sample size of 13 and 14 for the first and second stage, respectively, will provide an overall one-sided alpha value of 0.05 and statistical power of 0.80 when the true ORR is 0.20. If there is 1 or more response observed from the 13 patients in first stage, the study will proceed to the second stage. To account for potential patient drop-out, a total of approximately 30 patients will be enrolled in order to obtain evaluable data from 27 patients.

For the Arm B dose expansion period, the sample size estimation is based on Simon's two-stage design (Richard S, 1989). The null hypothesis that the true ORR is 0.1 will be tested, and the sample size of 15 and 26 for the first and second stage, respectively, will provide an overall one-sided alpha value of 0.05 and statistical power of 0.80 when the true ORR is 0.25. If there are 2 or more responses observed from the 15 patients in first stage, the study will proceed to the second stage. To account for potential patient drop-out, a total of approximately 45 patients will be enrolled in order to obtain evaluable data from 41 patients.

The planned study enrollment is approximately 117 patients. Approximately 57 patients will be enrolled during the Dose Escalation Period and Dose Confirmation Periods of the study. During the Expansion Period of the study, approximately 60 patients will be enrolled at the MTD/RDE.

4.2. Randomization and Blinding

Not applicable. It is an open-label study.

4.3. Analysis Set

4.3.1. Intent-to-Treat Set

The intent-to-treat (ITT) set will consist of all patients who are enrolled (i.e. signed informed consent form). Patients will be included in the dose cohort to which they were enrolled.

4.3.2. Safety Set

The safety set will consist of all enrolled patients who received any amount of study drug. Patients will be included in the dose cohort corresponding to the dose level which they actually received.

4.3.3. Activity Evaluable Set

The activity evaluable set will consist of all enrolled patients who received any amount of study drug and have at least 1 tumor response evaluation. Patients will be included in the dose cohort to which they were enrolled.

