10.10 RADIOLOGIC ASSESSMENTS

For the purpose of this clinical trial, the following imaging will be acquired at Screening for a baseline tumor assessment and on study:

- CT (with contrast) or magnetic resonance imaging (MRI) of the chest, abdomen and pelvis
- CT (with contrast) or MRI of the neck, if clinically indicated
- Bone scan if clinically indicated

- PET-CT (for lymphoma)

All patients will have tumor assessments performed within 28 days prior to C1D1, every 56 days from C1D1 (\pm 7 days), and during Disease Progression Follow-up Period at 90 and 180 days following the end of treatment (\pm 30 days).

At screening, all patients will undergo CT with IV contrast of the chest, abdomen and pelvis. MRI should only be used to evaluate sites of disease that are not adequately imaged by CT. If a patient is intolerant of iodine-based contrast agents, CTs may be performed without contrast. MRI may be used to evaluate sites of disease where a CT without IV contrast is not adequate. Visible skin lesions and easily palpable subcutaneous tumors may be measured by physical examination using a ruler or calipers. Bone scans should be performed within past 60 days prior to Cycle 1 Day 1. If the baseline bone scan is positive, scans should be repeated at Cycle 3 Day 1, Cycle 5 Day 1, at the end of Cycle 6, and during Disease Progression Follow-up Period at 90 and 180 days following the end of treatment (\pm 30 days).

For optimal evaluation of patients, the same methods of assessment and technique should be used to characterize each identified and reported lesion at baseline and during follow-up. Target lesions should be selected and measured as per RECIST guidelines (see [Appendix C](#) and [Appendix D](#)).

At the investigator's discretion, imaging studies may be repeated at any time if disease progression is suspected. Due to the possibility of pseudoprogression, patients will be permitted to continue with treatment beyond initial RECIST 1.1 or Cheson defined disease progression as long as they meet the following criteria:

- If, in the opinion of the investigator, he/she is continuing to receive clinical benefit as defined by:
 - Absence of clinical symptoms and signs (including worsening of laboratory values) indicating disease progression
 - No decline in ECOG performance status
 - Absence of rapid progression of disease or of progressive tumor at critical anatomical sites (e.g., cord compression) requiring urgent alternative medical intervention.

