13.2 SAMPLE SIZE CONSIDERATIONS

No formal sample-size estimation will be performed. The choice of the number of patients will be based on a standard, Phase 1, 3+3 dose escalation design in which 3 to 6 patients are enrolled into each dose cohort.

For the Arm A dose expansion period, the sample size estimation is based on Simon's minimax two-stage design (Richard S, 1989). The null hypothesis that the true overall response rate is 0.05 will be tested, and this design with the sample size of 13 and 14 for the first and second stage, respectively, will provide an overall one-sided alpha value of 0.05 and statistical power of 0.80 when the true overall response rate is 0.20. If there is 1 or more response observed from the 13 subjects in first stage, the study will proceed to the second stage. To account for potential patient drop-out, a total of approximately 30 patients will be enrolled in order to obtain evaluable data from 27 patients. If four or more responses are observed in the 27 evaluable patients, mRNA-2416 will be considered active in ovarian cancer patients, and may warrant further development.

For the Arm B dose expansion period, the sample size estimation is based on Simon's two-stage design (Richard S, 1989). The null hypothesis that the true overall response rate is 0.1 will be tested, and this design with the sample size of 15 and 26 for the first and second stage, respectively, will provide an overall one-sided alpha value of 0.05 and statistical power of 0.80 when the true overall response rate is 0.25. If there is 2 or more responses observed from the 15 patients in first stage, the study will proceed to the second stage. To account for potential patient drop-out, a total of approximately 45 patients will be enrolled in order to obtain evaluable data from 41 patients. If eight or more responses are observed in the 41 evaluable patients, mRNA-2416 in combination with durvalumab will be considered active in ovarian cancer patients, and may warrant further development.

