13.4.3 EFFICACY ANALYSES

The Activity Evaluable Population will be used for the analyses of efficacy data based on the dose of mRNA-2416 received.

Best response will be determined for each patient in accordance with RECIST 1.1, and Cheson guidelines and the objective response rate presented for each dose cohort. The overall objective response rate based on irRC or LYRIC will also be determined. The disease control rate based on RECIST 1.1 will also be

determined for Phase II patients. Progression-free survival and durability of response will be determined using Kaplan-Meier methodology. Please refer to [Appendix C and D](#) for a description of “Immune-related Response Criteria,” and RECIST 1.1 criteria.

The details of Simon’s two-stage study design and analysis used for Arm A and Arm B Phase II will be included in the Statistical Analysis Plan (SAP).

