7.3.4. Treatment Modifications

Number of patients with mRNA-2416 injection administered, number of patients without mRNA-2416 injection administered, reason for mRNA-2416 injection not administered, number of patients who had dose modified, categories of dose modification, reason for dose modified, number of lesion injected, and

lesion type will be summarized by scheduled visits, treatment arm and dose cohort for Phase I and Phase II, and total for each treatment arm combining Phase I and Phase II.

Number of patients with durvalumab administered, number of patients without durvalumab administered, action taken with durvalumab, and reason for action on durvalumab will be summarized by scheduled visits and dose cohort for Phase I and Phase II, and total for Arm B combining Phase I and Phase II.

8. Efficacy Analysis

All tables and figures for efficacy evaluations will be conducted using the activity evaluable set by treatment arm and dose cohort (as specified in Section 3.3) for Phase I and Phase II, and total for each treatment arm combining Phase I and Phase II. Listings will be based on the safety set.

Solid tumor response will be assessed by investigators based on RECIST 1.1 (complete response [CR], partial response [PR], stable disease [SD], progressive disease [PD], or not evaluable [NE]), and based on irRC (immune-related complete response [irCR], immune-related partial response [irPR], immune-related stable disease [irSD], immune-related progressive disease [irPD], or not evaluable [NE]). Lymphoma response will also be assessed by investigators based on Cheson 2014 criteria (positron emission tomography [PET]-CT-based complete metabolic response, partial metabolic response, no metabolic response, or progressive metabolic response; CT-based complete radiologic response, partial radiologic response, SD, or PD), and based on LYRIC (PET-CT-based complete metabolic response, partial metabolic response, no metabolic response, progressive metabolic response, or indeterminate response; CT-based complete radiologic response, partial radiologic response, SD, PD, or indeterminate response). Best overall response is determined from time-point overall response. When SD for RECIST 1.1 or irSD for irRC is believed to be the best overall response, it must meet the minimum time (at least 55 days between the first dose date and the last SD assessment date, and no PD between). Death may be considered in determination of best overall response.

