8.1. Overall Response Rate

ORR is defined as the proportion of patients whose best overall response is partial response or better based on each corresponding criterion. If data allow, ORR may be summarized with Clopper-Pearson 95% confidence intervals (CI). No confirmation is required for partial response or better.

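### The Phase II primary ORR leaves out treated patients who never have a post-baseline tumor evaluation, which biases it upward and can take the two-stage false-positive rate above 0.05

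*SAP*

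**What the plan says.** SAP 4.3.3 defines the activity evaluable set as "all enrolled patients who received any amount of study drug and have at least 1 tumor response evaluation". SAP 8 then states: "All tables and figures for efficacy evaluations will be conducted using the activity evaluable set". The protocol agrees in 13.4.3: "The Activity Evaluable Population will be used for the analyses of efficacy data based on the dose of mRNA-2416 received". The ITT and safety sets are defined, but no ORR table is planned on either. The safety set serves efficacy listings only.

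SAP 8.1 says "ORR is defined as the proportion of patients whose best overall response is partial response or better based on each corresponding criterion". It has no rule for a treated patient who was never scanned. SAP 8 adds "Death may be considered in determination of best overall response", without saying how.

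The two-stage rules are in protocol 13.2, with the stage sizes also in 8.2.5 and 8.2.6. They are written for evaluable patients, a term the documents define only for DLT assessment (8.4.4). For Arm A, "The null hypothesis that the true overall response rate is 0.05 will be tested", and "a total of approximately 30 patients will be enrolled in order to obtain evaluable data from 27 patients". Arm B has a null of 0.10 and enrols about 45 to reach 41.

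Tumor assessments fall "within 28 days prior to C1D1, every 56 days from C1D1" (protocol 10.10). The Schedule of Events adds one at the End of Treatment visit.

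**The concern.** Membership of the analysis set depends on what happens to the patient after treatment starts. A treated patient who dies, or is lost, before any post-baseline evaluation cannot have a recorded response. Leaving that patient out removes a certain non-responder, so the effect on ORR goes one way only. If evaluable in the two-stage rules carries the SAP 4.3.3 meaning, the same patient is also left out of the stage 1 and final counts and made up from the drop-out allowance.

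The sentence on death in SAP 8 does not repair this. It is permissive, it concerns how best response is derived, and it does not bring an unscanned patient into the set.

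What is at stake is the Phase II primary endpoint and the rule by which each regimen is called active in ovarian cancer. That conclusion is about patients given the treatment. The estimate is about those who lasted long enough to be assessed.

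**Working it through.** **Inputs (protocol 13.2).** Arm A: n1 = 13, continue with at least 1 response, n = 27, success with at least 4, p0 = 0.05, p1 = 0.20. Arm B: n1 = 15, continue with at least 2, n = 41, success with at least 8, p0 = 0.10, p1 = 0.25. Stated for both: one-sided alpha 0.05, power 0.80. Drop-out allowance: 3/30 = 10.0% and 4/45 = 8.9%.

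**Step 1: the plan's own figures.** With r1 and r the numbers of responses needed at stage 1 and at the end, and n2 = n − n1, the exact probability of success at response rate p is

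P(p) = Σ (x = r1 to n1) C(n1, x) pˣ (1 − p)ⁿ¹⁻ˣ × Pr[Bin(n2, p) ≥ r − x].

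- Arm A: P(0.05) = 0.0416, P(0.20) = 0.801.
- Arm B: P(0.10) = 0.0430, P(0.25) = 0.803.

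The stated design is reproduced. Attained alpha is below 0.05 because the counts are discrete.

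**Step 2: effect of leaving out unscanned patients.** Let d be the share of treated patients with no post-baseline evaluation. The documents do not give it, so a range is shown. Assume all such patients are non-responders and are replaced until n evaluable patients are reached. If the response rate among treated patients is p0, the rate among evaluable patients is p0/(1 − d). At the allowance this is 0.05/0.900 = 0.0556 (Arm A) and 0.10/0.911 = 0.1098 (Arm B). Alpha is P(p0/(1 − d)).

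| d | Arm A: rate in evaluable | Arm A: alpha | Arm B: rate in evaluable | Arm B: alpha |
|---|---|---|---|---|
| 0 | 0.0500 | 0.0416 | 0.1000 | 0.0430 |
| 5% | 0.0526 | 0.0487 | 0.1053 | 0.0553 |
| Allowance (10.0% / 8.9%) | 0.0556 | 0.0573 | 0.1098 | 0.0674 |
| 15% | 0.0588 | 0.0679 | 0.1176 | 0.0926 |
| 20% | 0.0625 | 0.0810 | 0.1250 | 0.1206 |
| 30% | 0.0714 | 0.1176 | 0.1429 | 0.2050 |

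**Step 3: break-even.** Alpha reaches 0.05 when the evaluable rate is 0.0531 in Arm A (d = 5.8%) and 0.1031 in Arm B (d = 3.0%). As a guide, one unscanned treated patient on the way to 27 or 41 is 1/28 = 3.6% or 1/42 = 2.4%, below break-even. Two are 2/29 = 6.9% or 2/43 = 4.7%, above it.

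**Step 4: effect on a just-positive result.** If the whole allowance were treated and unscanned, 4/27 = 14.8% would be 4/30 = 13.3% of treated patients, and 8/41 = 19.5% would be 8/45 = 17.8%.

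**Step 5: check of possible fixes.**
- Existing cut-offs on the first 13/27 and 15/41 treated patients, unscanned counted as non-responders: alpha 0.0416 and 0.0430, power 0.801 and 0.803, as in step 1.
- Cut-offs of 4 and 8 carried to 30 and 45 patients: alpha 0.0563 and 0.0652.
- Cut-offs raised by one, 5/30 and 9/45: alpha 0.0150 and 0.0289, power 0.731 and 0.791.

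**The case against.** A reader might infer that the false-positive rate does exceed 0.05. The documents do not support that as an unconditional statement, for three reasons.

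- The designs start at 0.0416 and 0.0430, so some loss is absorbed, and the unscanned share is not given.
- The allowance counts enrolled patients. SAP 4.3.1 defines enrolment by signed consent, and protocol 13.1 foresees patients enrolled but never treated. Never-treated patients do not inflate alpha against a null for treated patients. If two of Arm A's three losses and three of Arm B's four were never treated, d is 3.6% and 2.4%, both under break-even.
- If the nulls of 0.05 and 0.10 are meant for evaluable patients, alpha holds and only the question of what ORR describes remains.

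A reader might also infer that everyone who stops before Day 56 is dropped. That too goes too far. The End of Treatment visit, due within 14 days (±2) of the decision to stop, includes a tumor assessment, and protocol 10.10 allows imaging whenever progression is suspected. Patients assessed in these ways stay in. SAP 8 lists NE among the responses, so a patient with an unevaluable scan may also stay in as a non-responder, though the SAP does not say so. Eligibility requires ECOG 0–1 and at least 12 weeks (84 days) of life expectancy, past the first scan at Day 56 ± 7, so heavy early loss should not be presumed.

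Finally, SAP 5.1 tabulates analysis sets and discontinuation reasons, and efficacy listings use the safety set, so losses will be visible. The aim is also modest: preliminary activity that may justify further development.

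All of this stands as a limit on the size. It does not remove the bias. Patients who die, are lost or are too ill to attend before any evaluation remain outside the primary ORR, and a listing changes neither the primary estimate nor the decision count.

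**Conclusion.** The point holds in conditional form and should be fixed. As an estimate for treated patients, the primary ORR is biased upward whenever a treated patient goes without a post-baseline evaluation, by a factor 1/(1 − d). That follows from the definitions alone.

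The effect on error rates rests on three assumptions: evaluable in the two-stage rules means the activity evaluable set, the nulls apply to treated patients, and unscanned patients are replaced. Under these, alpha passes 0.05 once more than about 5.8% (Arm A) or 3.0% (Arm B) of treated patients are unscanned. It would be about 0.057 and 0.067 if the entire drop-out allowance were treated, unscanned non-responders. That is an illustrative case, because part of the allowance may never be treated. The larger values in the table belong to assumed losses for which the documents give no source.

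**What to change.** In SAP 4.3.3, 8 and 8.1 and protocol 13.2 and 13.4.3:

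- Make all treated Expansion patients the primary ORR set, and count a patient with no post-baseline tumor evaluation as a non-responder, whatever the reason.
- Define evaluable the same way for the two-stage rules. Apply at least 1/13 and 4/27 (Arm A), and at least 2/15 and 8/41 (Arm B), to the first 13/27 and 15/41 treated patients. The drop-out allowance then covers only patients enrolled but not treated.
- Do not carry the cut-offs of 4 and 8 over to 30 and 45 patients. That gives alpha 0.056 and 0.065, about the inflation the change is meant to remove.
- Keep the activity evaluable set as a supportive analysis, and state whether an NE assessment qualifies a patient for it.

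The cost is wording in two documents and a slightly lower reported ORR. No new data are needed. The power of 0.801 and 0.803 applies if the targets of 0.20 and 0.25 are rates among treated patients. If they were set for scanned patients, power would be somewhat lower.
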